3.3. Reporting Procedures

3.3.1. Adverse Event Reporting

Index Procedure and during 6-month Follow-up

All AEs that occur either during the injection procedure or during the 6-month follow-up phase of the study will be documented as described above as soon as possible upon knowledge of the event.

3.3.2. Investigator responsibilities

Independent Ethics Committees Reporting

Report to the IEC by The principal investigator(s) must report to the IEC all reportable events, as required by the clinical study protocol or by the IEC.

4. Risk evaluation

4.1. Potential Risks to Study Subjects

Subjects in this study are exposed to potential risks associated with aspiration of joint fluid, and solution injection into the thumb joint. These include pain, bleeding, bruising, infection, deep venous thrombosis, scar tissue formation, thrombotic complications and nerve damage. These risks are not unique to this study and may occur with any aspiration, or joint injection procedure. The use of joint splinting could create discomfort, venous or lymphatic stasis present in the relevant hand.

4.2. Investigation Suspension or Termination

The Investigator, the IEC, may suspend or terminate the investigation at any/all investigational sites at any time if they believe:

- There is unacceptable risk to the subjects enrolled in the study
- Failure of the investigator to enroll patients into the study at an acceptable rate
- Failure of the investigator to comply with the protocol or appropriate regulations, especially with respect to subject safety
- Site personnel knowingly submit false information from the investigative site to the study monitor, or IEC.

4.3. Potential Benefits of the Procedure

The potential benefit of OOT and joint splinting for the treatment of thumb OA includes symptomatic pain relief, hand function restoration, and anatomical improvement within the joint.

4.4. Bias Minimization

4.4.1. Randomization

The randomization plan will be produced using SAS v 9.4 or similar software. Balanced randomization with random block sizes (1:1, OOT plus splint:only splint) will be implemented. In the event that, post-randomization, no study treatment was given, randomization will not be reassigned and in this case will not count toward the overall sample size. Randomization will continue with the next case enrolled until the minimum sample size of 20 subjects is reached in both treatment groups. Subjects that have signed informed consent and are in screening process when the minimum study sample size is reached, will be randomized and treated per protocol provided that they found to be eligible. The enrollment activities will be monitored closely to limit number of these subjects. Randomization will be stratified by site, and each site will receive separate randomization plans using random predetermined block sizes that will remain undisclosed to the sites. The randomization file will be uploaded into the electronic data capture (EDC) system. Once the subject is enrolled into the EDC and has been identified as eligible for randomization, the randomization allocation will be visible within the EDC and viewable only by the un-blinded research associate. The subject will be treated according to the contents of the displayed randomization allocation.

5. Data collection, handling and retention

5.1. Source Documentation

Source documentation for this study will be maintained to capture the course of treatment and to substantiate trial data integrity. Source documentation will include, but is not limited to, worksheets, hospital and/or clinic or office records documenting subject visits including study procedures and other treatments or procedures, medical history and physical examination information, imaging results, device accountability records, medical consultations and laboratory results and reports.

5.2. Case Report Forms

Data for this clinical trial will be collected and documented on the subject's CRFs. CRFs provided may appear in paper or electronic form. Only authorized study site personnel or subjects will complete CRFs as appropriate to the specific CRF. CRFs must be reviewed and signed by the investigator or their documented designees. This may be done electronically within the electronic

data capture system. Because there is a potential for errors, inaccuracies, and misinterpretation in the process of transcribing data onto CRFs (whether paper or electronic), the following documents must be available at all times for inspection and comparison to the CRFs by the study monitor: data query forms, originals or photocopies/certified copies of all relevant records and reports, copies of test results and reports.

5.3. Records Retention

All CRF information, study records, reports and source documents that support the CRF must be retained in the files of the responsible investigator for a minimum 2 years following notification by designee that all investigations have been completed, and will further be retained in accordance with local and international guidelines as identified in the Investigator Site Agreement.

6. Reporting

6.1. End of Study Report

The investigator should notify the IEC in writing within three months after completion, termination, or discontinuation of the study at the site. The same procedure will be applied to regulatory authorities where required.

7. Statistical analysis

A complete Statistical Analysis Plan (SAP) will be finalized prior to database lock and unblinding. All statistical analyses will be performed according to valid, prospectively defined methods. Briefly, key planned analyses are described below.

7.1. Sample Size Calculation

The sample size is calculated on the basis of the study: Heyworth BE, Lee JH, Kim PD, Lipton CB, Strauch RJ, Rosenwasser MP. Hylan versus corticosteroid versus placebo for treatment of basal joint arthritis: a prospective, randomized, double-blinded clinical trial. *J Hand Surg Am.* 2008;33(1):40-48. doi:10.1016/j.jhsa.2007.10.009. In designing this injective clinical trial, a power analysis was performed to determine the sample size required to detect differences the size of 1 SD in the DASH outcome measure. A calculation of 16 patients per group was shown to demonstrate 80% power and a 5% 2-tailed type I error rate to detect DASH differences seen in previous studies investigating treatment of basal joint arthritis. To safeguard against loss to follow-up and other

unexpected variances, we determined that approximately 20 patients per group (40 patients in total) were needed to observe these clinically relevant differences.

7.2. Efficacy Analysis

Data were described as number and percentage, if categorical, or mean and standard deviation, if continuous, unless otherwise specified. Differences were described as mean, standard deviation and 95% confidence interval. Baseline characteristics were presented for the whole sample, while test values over time were presented only for patients who weren't lost to follow up.

Differences between groups were explored with chi square test, with Fisher correction if necessary, for categorical variables, or with Student t-test for continuous variables approximately Gaussian, or with Mann Whitney test otherwise. Adherence to Gaussian distribution were verified with Shapiro Wilks test.

About primary outcome, DASH and NRS were also described as percentage of patients reaching the minimal importance difference of 10.83 and 2 points, respectively.

Significance threshold was set to 0.05, all analyses were made with Stata version 18.

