1.7. Study Objectives

The primary study objective is to determine whether two injections of OO and thumb splint are superior to the use of only the joint splinting in reducing pain.

1) The primary study endpoint is to establish the improvement in DASH score from baseline.

2) Secondary objectives of this study are:

- Improvement in VAS Pain,
- Improvement in Grip Strength Function,
- Improvement in Tip Pinch Function.
- Improvement in the Kapandji Score.
- Improvement in the Nine-Hole Peg Test.

2. Investigational Plan

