2.4.1.3. Confirm Eligibility

Screening assessments include:

- DASH questionnaire for index thumb joint
- X-Ray

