2.4.6. Follow-up Visits

Follow-up assessment visits will be at the following intervals following the injection:

1 Month (\pm 7 days)

3 Month (\pm 7 days)

6 Month (\pm 7 days)

The following assessments and information will be collected at follow-up visits:

- DASH (all follow-up visits)
- VAS (all follow-up visits)
- Grip strength test (all follow-up visits)
- Tip pinch strength (all follow-up visits)
- Kapandji score (all follow-up visits)
- Nine-hole Peg test (all follow-up visits)
- Medication use (During the first 6-Month follow-up period, information on all medication usage will be collected)
- AEs (During the first 6-Month follow-up period, all AEs have to be reported.)

The study follow-up visits consist of a structured telephone interview and electronic self-report. The investigative center will contact the subject to complete the Follow-up, Adjunct Therapies and AE forms remotely.

Use of certain pain medication must be discontinued 48 hours prior to assessments (with the exception of aspirin taken for cardio protection). Aspirin in low dose would not be enough to affect any pain sensations. In addition, the low dose aspirin is supposed to be taken every day when taken for cardio-protection, so they should remain consistent on their regimen throughout the study. **In case of pain, it's possible to take Paracetamol 1000 mg 1 tablet (maximum dose 2 tablets per day).**

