7.3. Demographics and Medication Use

Subject demographics and medication use will be summarized and thoroughly characterized with descriptive statistics including error measures. Categorical variables will be summarized using frequency and percentage. Continuous variables will be summarized using mean, median standard deviation, minimum, and maximum. To assure that randomization was successful the following tests will be conducted; (1) age and baseline DASH comparisons of OOT and splint groups will be tested using two- tailed independent sample t-tests, (2) gender distribution will be tested using a Fisher's Exact test, and (3) Race distribution will be tested using a Likelihood-Ratio Chi-square test. Each of these three tests will be conducted using alpha = 0.05.

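### The primary DASH comparison uses neither baseline DASH nor site as a covariate, which usually costs precision; separately, no primary visit is named

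*Combined protocol and SAP*

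**What the plan says.** Section 1.7 states: "The primary study endpoint is to establish the improvement in DASH score from baseline". It names no visit. The screening assessments in section 2.4.1.3 include the "DASH questionnaire for index thumb joint", and section 2.4.6 and Appendix A schedule DASH again at months 1, 3 and 6.

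Section 7.2 compares groups on continuous variables "with Student t-test for continuous variables approximately Gaussian, or with Mann Whitney test otherwise". On reporting it says: "Differences were described as mean, standard deviation and 95% confidence interval". It lists no covariate and no primary visit. It also summarises the percentage of patients reaching a minimal important difference of 10.83 DASH points.

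Baseline DASH also appears in section 7.3, where "age and baseline DASH comparisons of OOT and splint groups will be tested using" t-tests as a check on randomisation. Section 4.4.1 says: "Randomization will be stratified by site". Site does not return in the analysis.

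The sample size in section 7.1 is set to "detect differences the size of 1 SD in the DASH outcome measure", giving 16 per group and 20 after an allowance for losses. Section 7 promises a complete SAP before database lock and unblinding. ANCOVA stands in the abbreviation list, but no section assigns it to an analysis.

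**The concern.** There are two separate matters.

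**Precision.** A patient's baseline DASH predicts the follow-up score. A change score removes the baseline with a fixed slope of 1. ANCOVA estimates the slope and so usually leaves less residual variance. In a trial of 40 patients, a narrower interval at no cost in data is worth having. The balance test in section 7.3 does not supply it, because it does nothing to the treatment estimate.

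**Primary visit.** With three DASH follow-ups and none named as primary, the result that counts could be picked after all three are seen. That affects type I error rather than precision, and baseline adjustment does not cure it.

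**Working it through.** **1. The plan's own figure.** Inputs from section 7.1: difference 1 SD, two-sided 5%, power 80%. Normal approximation: n = 2 × (1.960 + 0.842)² / 1² = 15.7, so 16 per group, as stated. With 20% loss, 16 / 0.80 = 20. By the noncentral t distribution, the unadjusted test has 78.1% power at 16 per group and 86.9% at 20.

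**2. Formulas.** Take the baseline SD as 1, the follow-up SD as k and the baseline–follow-up correlation as r. The documents give neither k nor r; both are assumed.

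- Variance of change: Vc = 1 + k² − 2rk.
- Residual variance under ANCOVA: Va = k²(1 − r²).
- Cost of estimating the slope: factor 1 + 1/(2n − 4), which is 37/36 = 1.028 at n = 20.
- For an effect of 1 SD of change, the noncentrality is √(n/2) = 3.162 for the change-score t-test (38 df) and 3.162 / √(1.028 × Va/Vc) for ANCOVA (37 df).

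**3. Power at 20 per arm, against 86.9% for the change-score t-test.**

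| k | r | Vc | Va | Va/Vc | ANCOVA power | Gain (points) |
|---|---|---|---|---|---|---|
| 1.0 | 0.30 | 1.400 | 0.910 | 0.650 | 96.5% | 9.6 |
| 1.0 | 0.50 | 1.000 | 0.750 | 0.750 | 93.9% | 7.0 |
| 1.0 | 0.70 | 0.600 | 0.510 | 0.850 | 90.9% | 4.0 |
| 1.0 | 0.85 | 0.300 | 0.278 | 0.925 | 88.5% | 1.6 |
| 0.8 | 0.30 | 1.160 | 0.582 | 0.502 | 99.0% | 12.1 |
| 0.8 | 0.50 | 0.840 | 0.480 | 0.571 | 98.0% | 11.1 |
| 0.8 | 0.70 | 0.520 | 0.326 | 0.628 | 96.9% | 10.0 |
| 0.8 | 0.85 | 0.280 | 0.178 | 0.634 | 96.8% | 9.9 |
| 1.3 | 0.30 | 1.910 | 1.538 | 0.805 | 92.3% | 5.4 |
| 1.3 | 0.50 | 1.390 | 1.268 | 0.912 | 88.9% | 2.0 |
| 1.3 | 0.70 | 0.870 | 0.862 | 0.991 | 86.2% | −0.7 |
| 1.3 | 0.85 | 0.480 | 0.469 | 0.977 | 86.7% | −0.2 |

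A simulation at k = 1 (100,000 trials per setting) gave ANCOVA power of 96.5, 93.9, 90.9 and 88.4%, in agreement. The 95% confidence interval was 18, 12, 6 and 2% narrower.

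At 16 per arm with k = 1, the same formulas give 91.5, 87.3, 83.0 and 79.8% against 78.1%.

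Section 7.1 does not say which SD it means. If 1 SD is that of the follow-up score, then at k = 1 and 20 per arm the change-score test has 74.0, 86.9, 97.8 and 100% power, and ANCOVA 89.0, 93.9, 98.9 and 100%.

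**4. Site.** The number of sites is not given. With 2 or 4 equal sites and an assumed intraclass correlation of 0.05–0.10, ANCOVA without site is conservative: simulated type I error is 4.1–4.7%, intervals are 2–5% too wide and power is 1–3 points lower. With one site nothing is lost.

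**5. Visit.** For three independent looks at 5%, the chance of at least one false positive is 1 − 0.95³ = 14.3%. Real visits are correlated, which lowers it. Simulating no effect with r from 0.3 to 0.7 and between-visit correlation of 0.5–0.7, the best of three visits gives about 10–13% with change scores and 11–13.5% with ANCOVA. The corner with r = 0.7 and between-visit correlation 0.5 reaches about 14% with either. Either test fixed at one visit holds about 5%.

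**The case against.** The strongest reply is that nothing here is invalid. A change-score test fixed at one visit holds its 5% level, and at 20 per arm it has 86.9% power for the planned effect, above the 80% target. The size of the gain rests on a correlation and an SD ratio that the documents do not give, and in part of the plausible range there is no gain. All of this stands, and it makes the precision point a recommended improvement rather than the repair of a fault.

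It can also be said that section 7 describes the analyses only in brief and defers to a complete SAP. That SAP could name both the covariates and the visit. But section 7 presents what follows as the key planned analyses, and section 7.4 refers to the SAP for exploratory analyses. The text available settles neither matter.

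Three stronger readings are tempting but not supported:

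- A reader might infer that the form of the outcome is open, so that switching between change and follow-up score adds further type I error. Section 1.7 defines the endpoint as improvement from baseline, and the 10.83-point responder summary most naturally refers to change as well. Testing the raw follow-up score would depart from the stated endpoint. Section 7.2 merely does not restate the form.
- A reader might infer that baseline DASH serves only the randomisation check. It also enters the endpoint itself and, most naturally, the responder summary. What is missing is its use as a covariate.
- A reader might take the 10–13% error as an argument for ANCOVA. It is not one, since the inflation is much the same with either analysis.

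**Conclusion.** The point holds in two parts. First, the primary DASH comparison is unadjusted although baseline DASH and the randomisation stratum are available. The planned change-score test is valid but usually less efficient. With equal SDs the gain from ANCOVA at 20 per arm runs from about 10 points of power at r = 0.3 to between 1 and 2 points at r = 0.85. It is larger if DASH is less variable at follow-up than at baseline, and can vanish, with a loss of under 1 point, if it is clearly more variable. These figures assume normal data, an effect of 1 SD of change, and the stated r and k. The contribution of site is small and depends on there being more than one.

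Second, no primary visit is named. This does not depend on the first part. If the visit were chosen after seeing the data, type I error would be about 10–13% under the assumed correlations. The documents do not show that such a choice was made; they do not rule it out.

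**What to change.** In section 7.2 and the SAP:

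1. Name one of months 1, 3 and 6 as the primary visit for DASH.
2. Make the primary analysis a linear model of DASH at that visit on treatment, baseline DASH and site (if there is more than one), and report the adjusted mean difference with its 95% confidence interval. With baseline in the model, the treatment estimate is the same whether the outcome is the follow-up score or the change, so the endpoint in section 1.7 is kept.
3. Keep the unadjusted test on change from baseline as a sensitivity analysis.

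The cost is wording, one degree of freedom for baseline and one for each site beyond the first. No new data or visits are needed. The change must be made before database lock and unblinding. Section 7.2 is written in the past tense; if the analysis has already been run, the adjusted model must be labelled post hoc.

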7.3. Demographics and Medication Use

Subject demographics and medication use will be summarized and thoroughly characterized with descriptive statistics including error measures. Categorical variables will be summarized using frequency and percentage. Continuous variables will be summarized using mean, median standard deviation, minimum, and maximum. To assure that randomization was successful the following tests will be conducted; (1) age and baseline DASH comparisons of OOT and splint groups will be tested using two- tailed independent sample t-tests, (2) gender distribution will be tested using a Fisher's Exact test, and (3) Race distribution will be tested using a Likelihood-Ratio Chi-square test. Each of these three tests will be conducted using alpha = 0.05.

7.4. Subject Reported Outcomes

Subject reported outcome measures: DASH, VAS, Grip Strength Test and Tip Pinch Strength test, Nine-Hole Peg Test, and Kapandji Score will be summarized and thoroughly characterized with appropriate descriptive statistics including error measures. Categorical variables will be summarized using frequency and percentage. Continuous variables will be summarized using mean, median standard deviation, minimum, and maximum.

These measures will also be analyzed using inferential statistics. Planned exploratory analyses, along with associated statistical tests, are described in the SAP.

7.5. Safety Analysis

The safety profile of OOT will be characterized by summarizing AEs, which will be standardized using the Medical Dictionary for Regulatory Activities. Characterization will include narratives of all SAEs and descriptive statistics including AE incidence overall and per subject, AE severity, AE device relatedness, and AE onset for each treatment group. AEs will also be used to characterize the safety of a repeat OOT injection. Results will be tabulated by treatment group.

8. Study monitoring and quality control

The investigational sites will be monitored to ensure compliance with the trial protocol, adherence to applicable regulations, and accuracy of trial data. Monitoring visits will be conducted primarily to ensure that the safety and wellbeing of the subjects is preserved. Monitoring visits will also be used to verify that trial data submitted on case report forms are complete and accurate with respect to the subject medical records and to verify device accountability. The principal investigator, his/her delegate(s) and the study coordinator(s) shall be accessible during monitoring. Accessibility is of particular importance for reviewing data in the CRF. Site personnel will complete CRFs following each subject visit. Trial data submitted will be reviewed against patient charts and other sources containing original patient records. As needed, intermittent monitoring visits will be conducted to compare data entered into the database to a selected sample of the subjects' source documents. Monitoring efforts will be expanded where the sample suggests irregularities.

Prior to the first site activation, a Monitoring Plan will be established outlining the activities above, as well as management of trial materials supplied to sites.

9. Ethical and legal considerations

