2.1. Study Design

This is a randomized, controlled, prospective evaluation comparing combined treatment with intra-articular ozone injections plus thumb splint with only the splint therapy. The maximum study duration for each subject will be 6 months. A total of 40 patients will be enrolled. These patients will meet specific inclusion and exclusion criteria, but can be generally characterized as patients with painful unilateral thumb OA who have been unable to achieve satisfactory pain relief with previous conservative OA treatment.

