2.5.2. Subject Discontinuation

Subjects will participate in the study until they complete the 6-months post treatment assessments. Subjects who do not complete the study per protocol may be exited from the study in the following manner:

Subject Voluntary Withdrawal

Subjects may withdraw their consent and discontinue participation in the study at any time for any reason or no reason, without jeopardizing their medical care. If a subject withdraws consent then it will be documented on the study exit form, and the reason for withdrawal will be requested.

Investigators must also report this to their respective Ethics Committee (EC) as defined by their institution's procedure and local EC requirements. No additional follow-up will be required and no additional data will be recorded from subjects once a subject has withdrawn from the trial. Subjects will not be replaced.

Subject Lost-to-Follow-up

In the event a subject cannot be contacted for post-treatment assessments, at least three attempts should be made to locate the subject and these efforts will be documented. Subjects will be

discontinued from the study if they are lost to follow-up. It should be understood that more than three attempts can be made, but three is the minimum required.

Investigator Withdrawal

Subjects may be withdrawn by the investigator prior to receiving an injection if, on the day of injection, it is determined by the investigator that the subject is no longer an appropriate candidate for injection (e.g., due to development of infection of the index joint) then the subject will be withdrawn from the study and will not receive the injection.

Subjects who are withdrawn from the study prior to receiving the index injection will be replaced. The investigator may decide to withdraw the patient from the study at any time based on medical judgment. In all instances of withdrawal, data collected up to the time of patient withdrawal may be used in the study. The site should complete a study exit form.

Endpoint Reached

Subjects who are not satisfied with the improvements in pain, function or stiffness following OOT or splinting treatment in the index thumb joint within 6 months and choose to seek additional treatment for their index trapezio-metacarpal OA will be discontinued from the study.

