2.6.6.2. Study Exit Form

This form will document termination of each subject's study participation and capture the reason for study exit.

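### Section 7.5 sets AE incidence side by side by arm without follow-up time, although dissatisfied patients can leave early and no AE contact is scheduled after exit

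*Combined protocol and SAP*

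**What the plan says.** **Safety analysis (7.5).** The plan is descriptive. It covers "AE incidence overall and per subject, AE severity, AE device relatedness, and AE onset for each treatment group", with narratives of all SAEs and a description of the safety of a repeat injection. "Results will be tabulated by treatment group". It defines no denominator, follow-up-time table, time-to-event summary or between-arm test. The opening of section 7 calls these analyses a brief account and promises a complete SAP before database lock.

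**AE collection (3.3.1 and 2.4.6).** "All AEs that occur either during the injection procedure or during the 6-month follow-up phase of the study will be documented". Section 2.4.6 likewise asks for all AEs over the 6 months, with remote contacts at Months 1, 3 and 6. Section 2.1 adds: "The maximum study duration for each subject will be 6 months".

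**Exit (2.5.2 and 2.5.3).** Patients who are dissatisfied with their improvement within 6 months and "choose to seek additional treatment for their index trapezio-metacarpal OA will be discontinued from the study". Section 2.5.3 makes additional treatment for the index thumb within 6 months a reason for the exit form, which will "capture the reason for study exit" (2.6.6.2). For voluntary withdrawal of consent, 2.5.2 states that "no additional data will be recorded from subjects once a subject has withdrawn from the trial".

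**Schedule (Appendix A).** The AE row runs through the Month 6 visit to the Study Exit column, and nothing follows exit.

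**The concern.** One route out of the study depends on response to treatment, which is what the trial expects to differ between arms. A patient who leaves at Month 2 can contribute no AE from Months 2 to 6 unless someone still asks. If more patients leave one arm, that arm is watched for less time, and a table of patients with an AE will tend to show fewer there even when the true risk is equal.

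Timing matters because not every event of interest belongs to injection day. Splints are worn for 2 months (2.4.5), and the device effects and risks listed in 3.1 and 4.1 include continuing joint ache, arthrosis beyond normal progression, scar tissue and nerve damage. Reporting AE onset shows when recorded events happened. It does not show how long each arm was observed. AEs that nobody asked about cannot be recovered at analysis.

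**Working it through.** **The plan's own figures.** The documents state no AE risk and no exit rate by arm, so there is no safety figure to reproduce. The arm size does reproduce. For a 1 SD difference, two-sided 5% and 80% power, n = 2 × (1.96 + 0.84)² / 1² = 15.7, so 16 per group (17 by the exact t-test). Then 16 / 0.80 = 20, an implied loss of about 20%.

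**Inputs**
- From the documents: 20 per arm (7.1), 6 months of follow-up (2.1).
- Assumed: the same true 6-month AE risk R in both arms, 20% or 40%; a share d leaving at month t = 1, 2 or 3; d of 10% in one arm and 30% or 40% in the other. The first pair averages 20%, equal to the implied loss; the second averages 25%, somewhat above it.

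**Formula.** Let F(t) be the risk of a first AE by month t. With no AE contact after exit, observed incidence = (1 − d) × R + d × F(t). The gap between arms is therefore (d₂ − d₁) × (R − F(t)), which is zero when exits are equal.

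**AEs spread evenly (constant hazard).** λ = −ln(1 − R)/6 and F(t) = 1 − exp(−λt). For R = 40%, λ = 0.0851 per month and F(2) = 15.7%.
- 10% exit at Month 2: 0.90 × 40 + 0.10 × 15.7 = 37.6%
- 30% exit at Month 2: 0.70 × 40 + 0.30 × 15.7 = 32.7%
- Gap: 4.9 points, or about one patient in 20 (7.51 against 6.54 expected)
- Follow-up: 20 × (0.90 × 6 + 0.10 × 2) = 112 person-months, against 20 × (0.70 × 6 + 0.30 × 2) = 96

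**AEs mostly early.** Put 80% of R in Month 1 and spread the rest evenly over Months 1 to 6, so F(t) = 0.8R + 0.2R × (t − 1)/5. For R = 40% and exits of 10% against 40% at Month 1, F(1) = 32%. Incidence is 0.90 × 40 + 0.10 × 32 = 39.2% against 0.60 × 40 + 0.40 × 32 = 36.8%, a gap of 2.4 points.

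**Range over exit months 1 to 3 and both exit pairs**

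| True 6-month risk | AEs spread evenly | AEs mostly early |
|---|---|---|
| 20% | 1.9 to 4.9 points | 0.5 to 1.2 points |
| 40% | 3.5 to 9.5 points | 1.0 to 2.4 points |

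The gap always lowers the arm with more exits.

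**Sampling error.** √(2R(1 − R)/20) = 12.6 points at R = 20% and 15.5 at R = 40%.

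**Would a rate per person-month cure it?** Under a constant hazard, yes: at R = 40% both arms have 8.51 first events per 100 person-months at risk. If AEs are early, no. Take 8 events in each arm, all before anyone leaves. Crude incidence is correctly equal, but 8/96 = 8.3 and 8/112 = 7.1 per 100 person-months, a spurious 17% excess (112/96 = 1.17) in the arm with more exits.

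**The case against.** Several stronger readings are tempting, and the documents do not support them.

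- *The plan tests AE incidence between arms, divides by 20 and counts unobserved months as AE-free.* Section 7.5 plans description only and states no denominator, and a fuller SAP is promised. What stands is that the present text does not account for follow-up time.
- *All recording stops when a dissatisfied patient leaves.* The explicit statement that no more data are recorded concerns withdrawal of consent only, and 2.4.6 and 3.3.1 ask for all AEs over 6 months. For dissatisfied patients the stop is an inference from discontinuation and the schedule. It is a fair inference, since no section provides for AE contact after such an exit.
- *The tables will flatter ozone.* If more splint-only patients leave, the splint arm looks safer and ozone worse. Nothing in the documents settles the direction.
- *The by-arm incidence table is the only safety result.* SAE narratives, severity, relatedness, onset and repeat-injection safety are planned too.

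The best argument against acting is size. Both injections fall within the first two weeks (Appendix A), and the AEs that section 3 anticipates are those of the injection procedure, so many should precede any exit. The gap is then at most half a patient in 20, well inside sampling error. It is also unclear how many would leave: 2.3 allows any medication needed after Month 1, apart from the listed intra-articular and surgical treatments, while 2.5.3 makes additional treatment within 6 months a reason for exit. All of this stands and keeps the point modest. It does not remove it, because the loss is systematic if exits differ, and onset and exit data alone cannot restore AEs that were never collected.

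**Conclusion.** The point holds as a modest, inexpensive improvement. Followed as written, the plan can miss later AEs unequally between arms and does not require the information that would let a reader see it. The distortion needs two conditions: exits that differ by arm, and AEs that occur after exit. Under the assumed exits it is about 2 to 10 percentage points with evenly spread AEs and about 0.5 to 2.4 points with mostly early AEs, against a standard error of about 13 to 15 points. The exit shares, AE risks and hazard shapes are all assumptions.

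A reader might infer that a rate per person-month is the remedy. It is not a safe one here: with early AEs it creates a difference in the opposite direction. A Poisson interval on all events would also treat repeat AEs in one patient as independent.

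**What to change.** **2.5.2 and Appendix A.** State that stopping study treatment or seeking other treatment does not end AE data collection. Keep the AE questions at whichever of the Month 1, 3 and 6 contacts remain, by telephone as already permitted, for every treated patient who has not withdrawn consent. List AEs that follow other treatment separately. Reconcile 2.3 with 2.5.2 and 2.5.3, so that it is clear which patients count as exits.

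**7.5.** Add by arm:
- follow-up time to last AE contact, and exit reasons;
- AE incidence in the first month beside the 6-month figure, each with its denominator (first-month incidence is unaffected by exits at Month 1 or later);
- time to first AE, censored at last AE contact. Exit related to response may make this censoring informative, so continued collection remains the main remedy.

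Any rate per person-month should be supplementary and split by period, for example Month 0–1 and Month 1–6. Its interval should not assume that repeat events in one patient are independent.

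**Cost.** A few telephone calls, a few lines of text and a few extra table rows. Exit forms and AE onset dates are already collected.
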